4.2 Secondary objectives

Describe the incidence of preoperative IDA.

5. Study aims

5.2 Primary outcome measure

DHb (pre-intervention Hb – post-intervention Hb)

5.2 Secondary outcome measures

Incidence of preoperative IDA in the elective paediatric surgical population in South Africa.

6. Methods

6.1 Study design

Prospective interventional quasi-experimental pre-post study across multiple hospitals in South Africa. Patients will be screened for trial eligibility at a normal routine outpatient clinic visit. Those patients with a screening Hb meeting the criteria for anaemia according to the WHO definition³⁰ and able to receive the oral iron for a minimum of 6 weeks prior to their planned operation, will be eligible for inclusion.

The formal laboratory blood test results will be reviewed within 48-76 hours by the research nurse to diagnose those patients who meet the pre-defined criteria for IDA. Parents & legal guardians will be contacted via telephone by the research nurse to inform them about their child's results and to instruct them to either discontinue or continue taking the oral iron supplementation dependent on whether the results meet the pre-defined criteria for iron-deficiency anaemia.

Prior to inclusion, freely given written informed consent must be obtained from all parents or legal guardians and assent from patients where appropriate.

6.2 Inclusion criteria

- Age > 6 months to <16 years
- Noncardiac surgery
- Elective surgery
- Anaemic as per WHO criteria¹

6.3 Exclusion criteria

- Patient or parent refusal
- Unable to obtain written consent at the surgical outpatient clinic
- Surgery planned in not less than 4 weeks from surgical outpatient visit
- Known history of acquired iron overload, family history of haemochromatosis or thalassemia
- Known reason for anaemia (e.g., untreated vitamin B₁₂ or folate deficiency or haemoglobinopathy)
- Treatment with oral iron, erythropoietin, IV iron therapy or blood transfusion in the previous 12 weeks
- Known hypersensitivity to oral iron or other contraindication to oral iron
- Temperature > 38.0 °C or receiving non-prophylactic antibiotics
- Acute liver failure

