Patient advocate

TBC

Sponsor

University of Cape Town

Funders

Society for the Advancement of Patient Blood Management

Table of Contents

1. LIST OF ABBREVIATIONS	4
2. SUMMARY	5
3. INTRODUCTION.....	6
4. STUDY OBJECTIVES.....	7
4.2 PRIMARY OBJECTIVE	7
4.2 SECONDARY OBJECTIVES	7
5. STUDY AIMS.....	7
5.2 PRIMARY OUTCOME MEASURE	7
5.2 SECONDARY OUTCOME MEASURES.....	7
6. METHODS	8
6.1 STUDY DESIGN	8
6.2 INCLUSION CRITERIA.....	8
6.3 EXCLUSION CRITERIA.....	8
6.4 SITE REQUIREMENTS	8
6.5 RESEARCH ETHICS AND INFORMED CONSENT	9
6.6 SUBJECT WITHDRAWAL.....	9
6.7 RECRUITMENT AND SCREENING	9
6.8 ENSURING ADEQUATE RESOURCES	10
6.9 CRITERIA FOR IRON DEFICIENCY	11
6.10 SUPPLEMENTAL IRON DOSING REGIMEN	11
6.11 EMPIRIC TREATMENT FOR WORMS.....	12
6.12 RESEARCH PROCEDURES, DATA COLLECTION AND COLLATION	13
6.13 DATASET.....	14
6.14 CASE RECORD FORMS.....	15
6.15 COLLECTION AND STORAGE OF BLOOD SAMPLES.....	15
6.16 MONITORING MEDICAL ADHERENCE	15
6.17 SAFETY REPORTING.....	16
5.10 EXPECTED BENEFITS TO INDIVIDUAL PARTICIPANTS AND POTENTIAL SOCIETAL BENEFITS ..	16
5.10 SAMPLE SIZE CALCULATION	17
5.10 POWER ANALYSES.....	17
5.11 STATISTICAL ANALYSIS.....	18
7. STUDY ORGANISATION AND MANAGEMENT	19
7.1 STUDY STEERING COMMITTEE	19
7.2 PATIENT ADVOCATE.....	19
7.3 LOCAL CO-ORDINATORS.....	19
7.4 TRAINING OF INVESTIGATORS	19
8. DATA MANAGEMENT AND OWNERSHIP.....	20
9. PUBLICATION PLAN.....	20
10. MANAGEMENT OF PREMATURE TERMINATION OF THE TRIAL.....	20
11. REFERENCES.....	21
10. APPENDICES	24

1. List of abbreviations

DHb	Delta haemoglobin (pre-treatment haemoglobin – post-treatment haemoglobin)
Hb	Haemoglobin
IDA	Iron deficiency anaemia
SAPSOS	South African Paediatric Surgical Outcomes Study

2. Summary

Short title	SAPSOS-2: Pilot Study
Methodology	Prospective national multi-centre interventional study
Research sites	Hospitals undertaking paediatric surgery in South Africa
Objective	To evaluate the efficacy of oral iron supplementation in children diagnosed with preoperative iron-deficiency anaemia undergoing noncardiac surgery.
Primary outcome	The delta Hb (DHb) (pre-intervention Hb –post-intervention Hb)
Number of patients	1110 patients
Inclusion criteria	Paediatric patients aged >6 months and <16 years admitted to participating hospitals undergoing elective non-cardiac surgery Anaemia as per WHO criteria ¹

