Studies investigating the impact of increasing preoperative haemoglobin on perioperative outcomes in children are primarily focused on blood loss and blood transfusion rates in surgery in which significant bleeding and frequent blood transfusion are anticipated and most children in these studies received preoperative erythropoietin²¹⁻²⁷. The impact of preoperative oral iron as a stand-alone intervention to increases preoperative Hb are limited to 2 studies^{28,29}. A single retrospective study has reported on the impact of the introduction of preoperative oral iron without EPO in children undergoing spinal surgery²⁸. They found a significant difference in intraoperative transfusion rates in patients who received a longer duration of preoperative oral iron therapy. The major limitation of the study was a lack of preintervention Hb, precluding the ability to assess the effect of iron supplementation on delta Hb.

A subsequent study reviewing the impact of preoperative oral iron in paediatric cardiac patients found that iron supplementation resulted in an increase in preoperative haemoglobin levels which was associated with reduced red blood cell transfusion volumes²⁹.

Given the high incidence of preoperative anaemia in children having surgery in South Africa in the public sector and its association with poorer postoperative outcomes, it is important to assess the feasibility of a pragmatic intervention to treat preoperative anaemia in the context of a resource-constrained setting. Although intravenous iron in combination with EPO may be more effective and have fewer side effects, oral iron is relatively inexpensive and widely available in South Africa. Regular deworming may also play an important role in the treatment of preoperative anaemia and has been shown to be an effective intervention to increase baseline Hb in school age children from low- and middle- income countries³⁰.

We hypothesise that the implementation of preoperative anaemia screening and treatment of anaemic patients with a minimum of 6 weeks supplementation with oral iron will have a clinically significant effect on increasing the haemoglobin in patients with preoperative IDA.

4. Study objectives

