6.12 Research procedures, data collection and collation

At recruitment phase

Eligible patients will be screened for anaemia with a finger-prick bedside Hemacue test at outpatient clinic. If the patient meets the WHO criteria for anaemia EMLA cream will be applied to potential sites for venepuncture and the patient will then be sent to the pathology laboratory for venepuncture with a request form for tests that will include laboratory full blood count (FBC), ferritin, transferrin saturation (TSAT), C-reactive protein (CRP), and reticulocyte Hb content. Patients who have not been dewormed within the last 6 months will be treated with mebendazole or albendazole as per the South African guidelines³³.

The patients age, weight, height, co-morbidities, ASA physical status, planned surgical procedure, planned date of surgery, severity of surgery, and type of surgery will be recorded. They will also be informed that they will be contacted telephonically once a week by the research assistant to enquire about compliance with the medication and enquire about any side-effects with the medication. The telephonic contact details will be confirmed by the research nurse and documented on the paper Outpatient CRF.

At home

The laboratory blood test results will be reviewed within 48 hours to diagnose those patients who meet the criteria for IDA. Any patients who do not meet the criteria will be contacted via telephone by the research nurse to instruct them to stop taking the iron supplementation and to bring the remaining iron supplementation with them to their next hospital visit. These patient folders and results for those patients not meeting the criteria for IDA will be reviewed by the appropriate surgical team to decide on appropriate ongoing management and further investigations which will be individualised to the patient.

For those patients meeting the criteria for IDA and continuing the oral iron supplementation, the parent or legal guardian will be contacted weekly to complete a short telephonic survey on compliance with the medication, side-effects, and to answer any questions or concerns they may have.

At time of Surgery

Repeat laboratory FBC at time of routine preoperative bloods if part of standard care.

Repeat ferritin, CRP, TSAT ± FBC whilst under anaesthesia prior to start of surgery.

Data collection

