6.13 Dataset

A realistic data set will be fundamental to the success of the investigation. This dataset will include the following:

All patients:

- Age (continuous, numerical)
- Sex (categorical, nominal)
- Weight (continuous, numerical)
- Height (continuous, numerical)
- Co-morbidities (categorical, nominal)
- Chronic medication (categorical, nominal)
- ASA Physical Status (categorical, ordinal)
- Severity of surgery (categorical, nominal)
- Type of surgery (categorical, nominal)
- Hemacue Hb

All anaemic patients

- Pre-intervention Hb (continuous, numerical)

- Pre-intervention MCV (continuous, numerical)
- Pre-intervention ferritin (continuous, numerical)
- Pre-intervention TSAT (continuous, numerical)
- Pre-intervention CRP (continuous, numerical)
- Pre-intervention reticulocyte Hb content (continuous, numerical)
- Syrup or tablet prescribed (categorical, nominal)
- Actual dose of elemental iron prescribed ($\text{mg}^{-1} \cdot \text{kg}^{-1} \cdot \text{day}^{-1}$)

All patients with IDA

- Post-intervention Hb (continuous, numerical)
- Post-intervention MCV (continuous, numerical)
- Post-intervention ferritin (continuous, numerical)
- Post-intervention TSAT (continuous, numerical)
- Post-intervention CRP (continuous, numerical)
- Post-intervention reticulocyte Hb content (continuous, numerical)
- Days of oral iron treatment (continuous, numerical)

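### The time-to-surgery exclusion is worded backwards, and its 4-week limit disagrees with the 6-week minimum in section 6.1 and the hypothesis, which neither inclusion list carries

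*Combined protocol and SAP*

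**What the plan says.** Four parts of the protocol bear on how far ahead surgery must be.

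- **Exclusion lists (Summary and section 6.3).** Both carry the same line: "Surgery planned in not less than 4 weeks from surgical outpatient visit".
- **Section 6.1, Study design.** Anaemic children who are "able to receive the oral iron for a minimum of 6 weeks prior to their planned operation, will be eligible for inclusion".
- **Hypothesis, end of section 3.** It concerns "treatment of anaemic patients with a minimum of 6 weeks supplementation with oral iron".
- **Inclusion lists (section 6.2 and Summary).** Section 6.2 has four items: age, noncardiac surgery, elective surgery, and "Anaemic as per WHO criteria". The Summary covers the same ground, with children "admitted to participating hospitals undergoing elective non-cardiac surgery". Neither list mentions time to surgery or duration of iron.

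Section 6.10 has the iron dispensed on the day of the clinic visit and taken until surgery, for up to 3 months.

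**The concern.** There are three linked faults.

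1. **Direction.** Not less than 4 weeks means 4 weeks or more. As an exclusion, the line removes children with time for treatment and keeps those without it.
2. **Threshold.** With the direction corrected, the lists start at 4 weeks, while section 6.1 and the hypothesis start at 6.
3. **Location.** The 6-week rule stands only in the design narrative and the hypothesis. The only time rule in the eligibility lists is the misworded 4-week line.

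Research nurses recruit at several hospitals (sections 6.4 and 6.8). One site could work to 4 weeks and another to 6, each with support in the protocol. A child enrolled at 5 weeks would satisfy the lists as intended and breach section 6.1. Time to surgery also limits how much iron a child can receive before the second haemoglobin measurement, and the primary outcome is the change in haemoglobin. The minimum exposure behind that outcome is therefore not fixed.

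**Working it through.** The plan gives no figure to reproduce here; the check is interval logic. Let *t* be the days from clinic visit to planned surgery, with 4 weeks = 28 days and 6 weeks = 42 days. Because iron starts on the day of the visit (section 6.10), both limits run on the same clock. The gap between them is not a lag before treatment starts.

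Rules:

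- Lists, exclusion read literally: excluded if *t* ≥ 28, so eligible if *t* < 28.
- Lists, exclusion read as probably intended: excluded if *t* < 28, so eligible if *t* ≥ 28.
- Section 6.1: eligible if *t* ≥ 42.

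| *t* (days) | Lists, literal | Lists, intended | Section 6.1 | 6.1 + literal | 6.1 + intended |
|---|---|---|---|---|---|
| 20 | in | out | out | out | out |
| 28 | out | in | out | out | out |
| 35 | out | in | out | out | out |
| 41 | out | in | out | out | out |
| 42 | out | in | in | out | in |
| 60 | out | in | in | out | in |
| 84 | out | in | in | out | in |

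Results:

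- **Literal wording with section 6.1:** *t* < 28 and *t* ≥ 42 cannot both hold, so no child qualifies.
- **Intended wording with section 6.1:** *t* ≥ 42. The 6-week rule governs and the 4-week line does nothing.
- **Intended wording, lists alone:** *t* ≥ 28. Children with 28 ≤ *t* ≤ 41 pass the lists and fail section 6.1.

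Shortfall of possible exposure in that band, against 42 days:

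- At *t* = 28: 42 − 28 = 14 days; 14/42 = 33.3%.
- At *t* = 41: 42 − 41 = 1 day; 1/42 = 2.4%.

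With the exclusion set at under 6 weeks, the lists give *t* ≥ 42, the same as section 6.1, and the band disappears.

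**The case against.** The strongest reply is that nobody would apply the line literally. The hypothesis and section 6.1 make the direction plain, so the reversal is a wording slip. Once it is turned round, the rules are compatible: eligibility conditions apply together, and the 6-week condition in section 6.1 is operative text placed directly before the lists. A child at 35 days is then simply ineligible. Harm requires staff to screen from the lists and overlook section 6.1, which the documents do not show. Sites are trained and complete a questionnaire before starting (section 7.4), and local co-ordinators supervise (section 7.3). Adherence is surveyed weekly and cross-checked by pill or syrup count (section 6.16). Days of iron are recorded for children with IDA (section 6.13) and are among the data to be analysed (section 5.11), so short exposure would be visible.

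Much of this stands. The empty eligible set follows only from the literal reading and is not a forecast of what sites will do. A reader who applies every section reaches 6 weeks. Actual exposure also depends on adherence and on when surgery really takes place.

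It does not remove the fault. The direction can be inferred, but the threshold cannot be inferred from the lists, and no text gives section 6.1 precedence over them. The training provisions do not say which limit is taught. Recording days of iron shows short exposure afterwards but does not say whether the child was eligible. Section 5.11 sets no minimum duration for the primary comparison.

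**Conclusion.** The concern holds and should be fixed. The exclusion is wrong as written in both places. Its 4-week figure disagrees with the 6-week minimum in section 6.1 and the hypothesis, and that minimum is missing from both inclusion lists.

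The practical size is a 14-day band, 28 to 41 days to surgery, in which the lists as intended and section 6.1 give opposite answers. Children in it could receive at most 67% to 98% of the stated minimum duration (28/42 to 41/42). This assumes that sites reverse the literal wording and that iron starts on the day of the visit.

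Two things cannot be judged. The documents give no distribution of waiting times, so neither the number of children affected nor any effect on power or on the haemoglobin change can be stated. The outpatient case record form (Appendix E) was not available, so how sites apply the rule is unknown.

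**What to change.** In the Summary and in section 6.3, replace the line with an exclusion such as: *planned surgery date less than 6 weeks (42 days) after the clinic visit*. This agrees with section 6.1 and the hypothesis. The nurse can check it at the visit, because section 6.12 already records "planned surgical procedure, planned date of surgery, severity of surgery" at recruitment.

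If the sponsor does intend 4 weeks, reword the exclusion to under 4 weeks and change section 6.1 and the hypothesis to match.

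The cost is one line in two places by protocol amendment, plus the screening form if it repeats the wording. No new data are needed. The downside of the 6-week rule is that some children with 4 to under 6 weeks to surgery would not be enrolled.

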6.4 Site requirements

Hospital sites will include public hospitals in South Africa performing elective paediatric surgery and each site must meet the following requirements:

- 1) Appointed research nurse able to obtain consent and perform finger-prick test at the surgical outpatient clinic.
- 2) On-site phlebotomy service.
- 3) On-site pharmacy able to provide the patient and parent or legal guardian with the oral iron supplementation and deworming medication where appropriate.

6.5 Research ethics and informed consent

Research ethics and regulatory approvals will be sought before starting the study at each site, in accordance with national research legislation/guidelines. Hospitals will not be permitted to record data unless ethics approval is in place.

Written informed consent (Appendix A) will be required for all study participants prior to screening haemoglobin is performed, with translators where necessary, from the primary parent or legal guardian or legally authorised representative and should include assent (Appendix B) of the child where appropriate. Two consent ± assent forms will be completed. One copy of the form(s) will be given to the parent or legal guardian to keep, and the other copy(s) will be kept in a study folder in a secure location.

The investigators will perform the study in accordance with this protocol, will obtain consent, and will report unanticipated problems involving risks to subjects or others in accordance with local ethics committee requirements. Collection, recording, and reporting of data will be accurate and will ensure the privacy, health, and welfare of research subjects during and after the study.

6.6 Subject withdrawal

Subjects may withdraw from the study at any time without prejudice to their care and will still be treated for their anaemia in accordance with standard treatment protocols.

6.7 Recruitment and screening

Eligible subjects will be identified at routine surgical outpatient appointments. Paper informed consent will be obtained prior to a finger-prick screening haemoglobin (Hemacue) is performed, with translators where necessary, from the primary parent or legal guardian or legally authorised representative and included assent of the child where appropriate. Broadcasting through an appropriate hospital notice will inform the patients, their parents/guardians and the public that the hospital is participating in the study (Appendix C).

The total patients planned to be recruited for screening is 1110 patients and these will be divided across 7 sites:

Sites		Number of patients to be screened	Estimated number of patients with IDA
Western Cape		460	18
Red Cross War Memorial Children's Hospital		310	12
Tygerberg Hospital		150	6
KwaZulu-Natal		250	10
Inkosi Albert Luthlui Hospital		150	6
Greys Hospital		100	4
Gauteng		400	16
Steve Biko Hospital		100	4
Kalafong Hospital		100	4
Chris Hani Baragwanath Hospital		100	4
Charlotte Maxeke Johannesburg Academic Hospital		100	4
Total		1110	44

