6.8 Ensuring adequate resources

To conduct a sound and valid study the investigators will ensure to the best of their ability that the following criteria are met:

- 1) Reasonable potential to recruit 1110 individuals to the study over a cumulative 9-month period.
- 2) An appropriate amount of time to complete recruitment, intervention, and data collection (9 months).
- 3) An adequate supply of suitably qualified staff at each facility including:
 - a) Appointed research nurse at each research site able to carry out the following responsibilities 3 days per week:
 - 08:00 to 10:00
 - Checking National Health Laboratory Services Results (NHLs) for blood tests at outpatient clinic
 - Telephonic follow-up with recruited patients to discontinue iron supplementation if they do not meet criteria for IDA
 - 10:00 to 16:00
 - Recruitment of patients for study
 - Obtaining written informed consent and assent where appropriate
 - Performing finger-prick Hb (Hemacue)
 - Applying EMLA for venepuncture for anaemic patients

Giving drug script signed by clinic doctor for oral iron supplementation ± deworming medication for collection at the hospital pharmacy

- b) Appointed research assistant for all sites to complete weekly telephonic survey for all IDA patients assessing medical adherence and side-effects, referring onto study nurse or doctor where appropriate.
- 3) Appropriate training on the study protocol, about any investigational product and about their duties to allow the staff to carry out their tasks safely and effectively.
- 4) Appropriate supervision of any individual or group to whom the investigator assigns trial-related duties at the trial site
- 5) Assurance that any person or party retained to perform trial-related duties is suitably qualified to perform those duties.

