5.10 Sample size calculation

How many patients will need to have a screening finger-prick Hb for the pilot study to be a representative of children undergoing noncardiac surgery with preoperative anaemia?

Secondary analysis of SAPSOS study found 46.2% patients were anaemic, using estimation for a single proportion with a specified precision and allowing for 10% drop out.

$$n = [p(1-p)z^2] / d^2$$

n: sample size

p: population proportion

z: 1.96, level of confidence, normal distribution

d: 0.05, acceptable margin of error

$$n = 0.46.(0.538)3.8416 / 0.0025 = 381.98$$

10% drop out rate: 38.2

Sample size: $382 + 38 = 420$

Given a sample size of 420 patients allowing for 10% drop-out approximately how many anaemic patients will be enrolled?

$$n = 420 * 0.90 * 0.462 \sim 176$$

[figure not shown]

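### The IDA incidence is worded for South Africa, but recruitment is a convenience sample at eight listed public hospitals with no rule for whom to approach and no stated log of those missed

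*Combined protocol and SAP*

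**What the plan says.** - **Target.** Section 5.2 (Secondary outcome measures) gives one secondary outcome: "Incidence of preoperative IDA in the elective paediatric surgical population in South Africa".
- **Sizing.** The section headed Sample size calculation (numbered 5.10) asks how many children need a screening Hb "for the pilot study to be a representative of children undergoing noncardiac surgery with preoperative anaemia". It answers with the single-proportion formula, using anaemia at 46.2% and a margin of 0.05.
- **Selection.** Section 6.7 says "Eligible subjects will be identified at routine surgical outpatient appointments". It adds "The total patients planned to be recruited for screening is 1110 patients and these will be divided across 7 sites", while its table lists eight hospitals in three provinces with planned numbers from 100 to 310. No basis for the split is given.
- **Staffing.** Section 6.8 provides for "Appointed research nurse at each research site able to carry out the following responsibilities 3 days per week", with recruitment from 10:00 to 16:00. It does not say which days or which surgical clinics are covered.
- **Sites.** Section 6.4 limits sites to public hospitals.
- **Records.** Under 6.12, case record forms are completed for recruited patients. Consent comes before the finger-prick test (6.5, 6.7), so a child who declines or is not approached has no Hb.
- **Analysis.** Section 5.11 gives no method for the incidence estimate: no confidence interval, no weighting by hospital and no reporting by hospital.

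**The concern.** A proportion depends directly on who enters the denominator. The plan sizes the study as if children were drawn at random from a defined population, but it describes recruiting whoever is identified in clinic while the nurse is there. Without an approach rule, inclusion may be related to iron status, for example through the specialty clinics covered, the families who agree, or the children who seem most relevant to an anaemia study. A larger sample does not reduce such a bias. Without a record of eligible children who were missed or declined, its likely extent cannot be judged afterwards.

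There is also a gap between target and sample. A figure pooled over hospitals in proportion to planned numbers describes those hospitals in that mix. It does not describe the country, and it excludes the private sector.

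**Working it through.** **1. The plan's own figure.** n = p(1−p)z²/d² = 0.462 × 0.538 × 3.8416 / 0.0025 = 381.94. The plan prints 381.98, then 382 + 38 = 420 for 10% dropout, so the figure reproduces. Its ±5 points is the margin for anaemia at 46.2% with n = 382. No corresponding calculation is made for IDA.

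**2. Make-up of the pooled figure.** The eight listed numbers add up: 310 + 2 × 150 + 5 × 100 = 1110. The largest hospital contributes 310/1110 = 27.9%, and each of the five smallest 100/1110 = 9.0%.

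**3. Recruiting pace.** Section 6.8 requires "Reasonable potential to recruit 1110 individuals to the study over a cumulative 9-month period". Taking nine months as 39 weeks, 8 hospitals × 3 days × 39 weeks = 936 nurse-days, and 1110/936 = 1.19 children per nurse-day. By hospital this runs from 100/117 = 0.85 to 310/117 = 2.65. The nine months also cover intervention and data collection. With an assumed 33 or 26 weeks of screening, the average becomes 1.40 or 1.78. Clinic volume is not given, so the share of eligible children this represents cannot be computed.

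**4. Values for IDA.** I take incidence as IDA per child screened.
- The columns "Number of patients to be screened" and "Estimated number of patients with IDA" in 6.7 total 1110 and 44, so 44/1110 = 4.0%.
- The power table treats the IDA share of anaemia as unknown and runs from 0.2 to 0.5. Multiplied by 46.2%, shares of 0.2, 0.3 and 0.5 give 9.2%, 13.9% and 23.1%.
- These do not agree: 44/(1110 × 0.462) = 8.6% of anaemic children, below the table's lowest share. I therefore show the whole range.

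**5. Sampling error.** Half-width = 1.96 × √(p(1−p)/1110), treating the children as a simple random sample, as the plan's formula does. For p = 0.0396 this is 1.1 points. For anaemia at 46.2% it is 2.9 points.

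**6. Selection bias.** Let r be the probability that a child with IDA is included, divided by that for a child without IDA. The expected observed proportion is rp/(rp + 1 − p), and the bias is that value minus p. For p = 0.231 and r = 1.5: 0.3465/(0.3465 + 0.769) = 0.311, a bias of +8.0 points. All values of r are assumptions.

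| IDA per child screened | Half-width | r = 0.67 | r = 1.25 | r = 1.5 | r = 2 | r needed for +5 points |
|---|---|---|---|---|---|---|
| 4.0% | ±1.1 | −1.3 | +0.9 | +1.9 | +3.7 | 2.39 |
| 9.2% | ±1.7 | −2.9 | +2.0 | +4.0 | +7.7 | 1.63 |
| 13.9% | ±2.0 | −4.1 | +2.9 | +5.6 | +10.5 | 1.44 |
| 23.1% | ±2.5 | −6.3 | +4.2 | +8.0 | +14.4 | 1.30 |

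At r = 1.5 the bias exceeds the sampling half-width in every row. At r = 1.25 it does so in all rows except 4.0%.

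**The case against.** **Arguments that the point is minor.** This is a pilot whose primary outcome is within-child change in Hb, and that comparison does not need a population sample. The nurse does not know the study Hb when approaching a family. Febrile children and those on non-prophylactic antibiotics are excluded, which limits selection on looking unwell. Age, sex, comorbidities, ASA status, and type and severity of surgery are recorded, so reporting by hospital and standardising to an outside case mix remain possible. The study file may hold further documents, and the contents of the case record forms are not shown, so the absence of a log is inferred from silence.

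Most of this is fair, and it limits the point to the secondary outcome. It does not supply an approach rule, and standardisation cannot correct selection on unmeasured factors.

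**Stronger readings that the documents do not support.**
- *That bias in IDA exceeds the planned ±5 points.* That margin belongs to anaemia. At 4.0% IDA, a rise of 5 points needs r of about 2.4, and a fall of 5 points is impossible.
- *That 1.25 times the odds of being approached would move anaemia by more than 5 points.* The formula needs a ratio of inclusion probabilities. If half of the non-anaemic children were approached, an odds ratio of 1.25 is a probability ratio of 0.556/0.5 = 1.11, and 46.2% becomes 48.8%, a shift of 2.6 points.
- *That about 1.2 children a day leaves the nurse wide choice.* Without clinic volume and after the eligibility limits, one child a day could be most of those eligible.
- *That some clinics are never sampled, or that the hospital numbers are fixed quotas.* The three days are not said to be fixed, and the numbers are planned totals with no stated cap.

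**Conclusion.** The point holds for the secondary outcome. As written, the recruitment is a convenience sample that cannot carry a national IDA incidence, and the plan states no means of assessing selection afterwards. The sampling half-width at n = 1110 is about ±1.1 to ±2.5 points for IDA between 4.0% and 23.1%. An assumed inclusion ratio of 1.5 would add about +1.9 to +8.0 points, more than the sampling error throughout that range.

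This shows how sensitive the estimate is. It does not predict a bias: the documents give no approach or refusal rates, so the ratio and its direction are unknown. The primary paired Hb comparison is not affected. The change is worth making before recruitment starts, because a log of missed children cannot be recreated later.

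**What to change.** - **Section 6.7, approach rule.** In each session worked, approach children who meet the criteria other than anaemia consecutively, or take every k-th child on the clinic list. Vary the starting point so that early arrivals are not favoured. Spread the sessions over the surgical clinics where this fits the nurse's existing duty to review laboratory results, which 6.12 sets at 48 hours.
- **Section 6.7, log.** Keep one line (age band, clinic, reason) for each eligible child not approached or declining.
- **Section 6.7, site count.** Reconcile the stated seven sites with the eight hospitals listed.
- **Section 5.2.** Word the outcome for children attending the participating public hospitals.
- **Section 5.11.** Report the IDA proportion by hospital and pooled, with a confidence interval, and state the denominator.

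The cost is a protocol paragraph, a short log and a less flexible nurse schedule. No additional procedure on any child is needed.
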